5.1.3 Planned statistical methods

The primary analyses are performed following the intention-to-treat principle. Additionally, per-protocol analysis will be performed for sensitivity analysis. We study the ratio of positive outcomes in both study arms by performing a Bayesian A/B test after every 40 additional patients, using the method described by Gronau et al.[53]. Data collection (and the periodical analysis of these data) will continue until a Bayes Factor of 10 (or 1/10) is achieved. The odds

ratio and its 95% credible interval will be reported. Covariates ICH volume, presence of intraventricular bleeding, do-not-resuscitate orders, location of hematoma and centre will be included in a Bayesian logistic regression model

Secondary analysis is performed on the secondary outcomes. For continuous variables, a Bayesian regression with normal error term is used, for time-to-event outcomes Bayesian cox-regression is used, and for binary variables Bayesian logistic regression is used. Statistical analysis is performed with R version 4.2.1 or higher (R core Team, 2022)[54]. A complete mRS shift analysis will be calculated.

In parallel to the Bayesian primary analysis, we will perform a frequentist test of proportions comparing study arm for the first 100 patients per study arm. In the ES arm, a number of explorative analyses are performed, studying the relation between hematoma location, hematoma size, and treatment outcome. In particular, for parameters measured over time, figures are created illustrating the development over time at both the patient level and group level.

5.1.4 Interim analysis

As described under “5.1.2.6. Conclusion of sample size estimation”, the data may be inspected any time, but we plan to perform the primary analyses after every 40 patients (20 per arm), and will stop data collection if the BF, in favor of either the null, or the alternative hypothesis is over 10.

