3.2 Primary and secondary outcomes

Primary outcome:

- Good functional outcome 6 months after treatment, measured by the mRS[33]. Good functional outcome is defined as a mRS of ≤ 3 points and will be assessed as binary outcome (yes/no, final value) at 6 months after treatment. The cut-off for good functional outcome is chosen at a mRS score of 3 points, as this reflects the turning point for a patient being able to live a partially self-dependent life or to live a severely disabled life. In this context, a mRS score of 3 points reflects the ability to walk unassisted and care for one's own bodily needs despite being moderately dependent on assistance, while a mRS score of 4 points describes a patient who is not able to walk anymore and needs assistance with all daily activities and thus marks a severe loss of patient autonomy.

Secondary outcomes:

- The mortality rate as measured by death of a participant (binary outcome (yes/no), final value) at 6 months after intervention.

- Patient reported outcome measures at 3 and 6 months after intervention, those being:
 - Patient and caregiver quality of life as assessed by the PROMIS® questionnaire (continuous variable, final value)
 - Patient Satisfaction as assessed by a short survey (Appendix 2) on a scale of 1-5 (continuous variable, final value)
 - Patient cognitive outcome as assessed by the MOCA® Test (continuous variable, final value)
- The morbidity rate, meaning occurrence of:
 - Ischemic stroke
 - Recurrent SSICH (defined as any radiologically confirmed increase in hematoma volume postoperative/follow-up that is either asymptomatic or associated with a worsening of the focal-neurological deficit by ≥ 4 points on the NIHSS and/or a decrease in consciousness by ≥ 2 points on the GCS)
 - Epileptic seizure
 - Surgical site infection (intervention group only)
 - Any need for open neurosurgical procedures
 - Infections (i.e. pneumonia, urinary tract infection)
 - Any other not defined complication that prolongs the hospital stay and/or leads to further treatment not envisaged in the original treatment plan.

The occurrence of any of these events 6 months after intervention (binary variable (occurrence/no occurrence), final value, proportion).

- The change of focal neurological deficit measured by the NIHSS, from baseline to 6 months after intervention as a continuous variable (continuous variable, change from baseline).

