5.1.2.6 Conclusion of sample size estimation

Based on these results we assume that we will likely be able to stop collecting data before reaching **75 patients per arm (total of 150 patients) to reach a BF of 10**. We aim to collect a minimum of 40 patients per study arm. From that point on, we will perform the abovementioned BF test after every 40 new patients (about 20 per arm, exact number subject to randomization). The evidence is regularly calculated until either a pre-set level of evidence threshold is achieved in favor of either of the hypotheses (BF of 10 or 1/10 respectively, considered as strong evidence), or when the maximum sample size is reached. For the current study, we chose to set the maximum total sample size at 200 (as deemed sufficient based on a frequentist sample size estimation for the same assumptions). If this threshold is not reached, a new cost-benefit analysis of continuing to collect data will be performed. However, as described above, this is highly unlikely. After data collection is deemed completed and follow-ups at 6 months are complete, all secondary and sensitivity analyses will be performed. For the data collected up to 40 per arm, a p-value may be calculated (sensitivity analysis) and used for a classical hypothesis test.

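### As written, the primary Bayes factor is fixed at the stopping look while some randomised patients still await their 6-month outcome, and no rule says which Bayes factor decides

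*Protocol*

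**What the plan says.** Section 3.2 defines the primary outcome as mRS of 3 or less, which "will be assessed as binary outcome (yes/no, final value) at 6 months after treatment". Section 4.3.6 allows a window of 7 weeks either side.

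On the looks, section 5.1.2.6 says "We aim to collect a minimum of 40 patients per study arm", with a test after every further 40 patients, and "we chose to set the maximum total sample size at 200". Section 5.1.4 describes the looks as the primary analyses and says the trial "will stop data collection if the BF, in favor of either the null, or the alternative hypothesis is over 10". Section 5.1.3 says that collection of data, and the periodic analysis of them, go on until the Bayes factor reaches 10 or 1/10.

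On what follows a stop, section 5.1.2.6 says: "After data collection is deemed completed and follow-ups at 6 months are complete, all secondary and sensitivity analyses will be performed". No section schedules a primary Bayes factor at that later point.

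On the analysis set, section 5.1.3 says: "The primary analyses are performed following the intention-to-treat principle".

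**The concern.** With an outcome read 6 months after treatment and no planned pause in recruitment, some randomised patients will have no mRS when a look crosses the threshold. The plan says what happens at the crossing (collection and the periodic primary analysis end) and what happens after complete follow-up (secondary and sensitivity analyses). Taken together, the primary Bayes factor is the one computed at the look, on an incomplete randomised set, while the secondary analyses would use a larger set.

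Two things are at stake. The primary result would not cover everyone randomised, although it is labelled intention to treat. And once the remaining outcomes arrive, a second Bayes factor can be computed. If it falls on the other side of 10, the protocol gives no rule for which value carries the conclusion, so the choice would be made with both values known.

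**Working it through.** **1. Patients awaiting outcome at a look.** Synopsis: first participant in 09/2023, last out 09/2028, so 60 months, or 54 months of accrual after subtracting 6 months of follow-up. Assume uniform accrual, no pause, and looks counted on observed outcomes.

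Number waiting = (N / accrual months) × follow-up months.

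- 200 over 54 months, 6 months: 200/54 × 6 = 22.2
- 200 over 60 months, 6 months: 20.0
- 150 (the expected size) over 54 months, 6 months: 16.7
- 150 over 60 months, 6 months: 15.0
- 200 over 54 months, upper end of the visit window (6 months + 7 weeks = 7.61 months): 28.2

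The range is 15 to 28, or about 8 to 14 per arm. At a look on all 200 outcomes nobody is waiting.

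**2. Reproducing the plan's own figure.** Section 5.1.2.3 uses the A/B test with package default priors. I took logit p1 = b − ψ/2 and logit p2 = b + ψ/2, with b and ψ both standard normal; this is an assumption. With control 0.50, risk ratio 1.6 and monitoring after every patient (4,000 trials), 89.6% to 91.0% reach a Bayes factor of 10 by 70 per arm, depending on when monitoring starts. Section 5.1.2.5 states about 90%. By 40 per arm I obtain 54% to 64%, against a stated 50%, so that figure is matched only roughly.

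**3. Effect of the waiting patients.** Looks at 40, 60, 80 and 100 per arm; stop at the first Bayes factor of at least 10; then recompute with 11 more patients per arm. There were 8,000 trials per row, and early means before 100 per arm. No simulated trial stopped for the null.

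| True rates | Early stops | Then below 10 | Then below 3 | Then below 1 |
|---|---|---|---|---|
| 50% vs 80% | 7,292 | 310 (4.3%) | 0.2% | 1 trial |
| 50% vs 75% | 6,007 | 500 (8.3%) | 0.6% | 0 |
| 50% vs 70% | 3,896 | 597 (15.3%) | 1.2% | 1 trial |
| 50% vs 65% | 1,965 | 453 (23.1%) | 3.2% | 1 trial |
| 50% vs 50% | 94 | 50 (53%) | 8.5% | 1 trial |

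With 8 or 14 more per arm, the share falling below 10 is 4.4% or 3.5% at 50% vs 80%, 15.2% or 15.7% at 50% vs 70%, and 20.9% or 21.7% at 50% vs 65%. So the result depends little on the assumed accrual when there is a benefit.

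The last row needs its denominator. Early stops under no difference are 94/8,000 = 1.2% of trials, and those falling back are 50/8,000 = 0.6%. With so few stops the 53% is imprecise: standard error √(0.53 × 0.47/94), about 5 points. It is 39% with 8 more per arm and 63% with 14.

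**The case against.** The strongest reply is that section 5.1.2.6 itself separates the end of data collection from the completion of 6-month follow-up. On that usage, stopping data collection means stopping enrolment. With the intention-to-treat statement, and section 4.4's wish (made about withdrawals) to analyse every last patient, one can argue that everyone randomised was always meant to enter the primary result. This stands in part. A reader might infer that the protocol excludes waiting patients, but no sentence does so and their follow-up is completed. What remains is that the protocol assigns each analysis to a time and gives the later time only to secondary and sensitivity analyses.

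A reader might also infer that the waiting patients could reverse the result. The figures do not support that. With 11 more per arm and a true benefit, the Bayes factor falls below 1 in at most 0.1% of early stops; the highest share seen is 0.2%, at 50% vs 65% with 14 more per arm. Slipping from just above 10 to just below it is a loss of strength, not a change of direction.

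It can be said that data cuts and overrunning patients belong in a statistical analysis plan, and section 5.1.6 refers to a detailed analysis plan that is not shown. That would answer pure silence. Here the protocol itself fixes the stopping rule and the timing of the analyses.

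Finally, section 5.1.2.2 holds that Bayes factors may be monitored without correction. Nothing here disputes that: the point is which patients enter the result, not whether a sequential penalty is due.

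**Conclusion.** The point holds as a badly fixed rule, not as a stated exclusion. Read as written, sections 5.1.2.6, 5.1.3 and 5.1.4 place the primary Bayes factor on fewer patients than were randomised and do not say which value decides once the rest report.

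The shortfall is about 15 to 28 patients, around 17 at the expected total of 150. It is not a figure in the protocol; it rests on uniform accrual, no pause, and looks counted on observed outcomes. At the design effect the consequence is small: about 4% of early stops drop below the threshold. It grows to 15% at 50% vs 70% and 21 to 23% at 50% vs 65%, and is about half under no difference, where only about 1% of trials stop early for the alternative. These shares also assume the standard normal priors, which the reproduced 90% supports.

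The change is worth making because it costs almost nothing and should be settled before the first look.

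**What to change.** - In sections 5.1.3 and 5.1.4, replace stopping data collection with stopping randomisation.
- State that looks count patients with an observed 6-month mRS.
- State that all randomised patients are followed to 6 months.
- Define the final primary intention-to-treat Bayes factor, odds ratio and 95% credible interval on all randomised patients, with the Bayes factor at the stopping look reported beside them.
- State in advance which of the two Bayes factors decides the conclusion.
- In section 5.1.2.6, say that the number randomised will exceed the look size by the patients awaiting outcome. Do not write in a fixed number, since it depends on actual accrual.

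The cost is wording only, because section 5.1.2.6 already provides for these follow-ups to be completed. The downside is that the final Bayes factor may fall slightly below 10 after the trial has stopped, and the report would have to say so.

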5.1.5 Stratification for outcome analysis

Explorative stratified subgroup analysis for potential confounders (ICH volume, presence of intraventricular bleeding, do-not-resuscitate orders, location of hematoma and centre) will be conducted using Bayesian logistic regression models. An analyses of gender differences is planned.

5.1.6 Deviations from statistical analysis plan

If substantial deviations of the analysis as outlined in these sections are needed for whatever reason, the protocol will be amended. All deviations of the analysis from the protocol or from the detailed analysis plan will be listed and justified in a separate section of the final statistical report.

5.2. Handling of missing data and drop-outs

If missing data occurs, we will try to obtain the respective data needed from either the participant, their next of kin or their treating physician. If acquiring the respective missing data is not possible, we will mark the data as missing. In case of missing laboratory values, we will aim to achieve them, if this proves to be impossible, the data will be marked as missing. In case more than 5% of patients show missing data for the primary outcome across arms, multiple imputation is performed.

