3.3.2 Methods of minimising bias

We plan to enrol a large enough sample to eliminate random error. Randomisation in 1:1 fashion should reduce any selection bias of patients due to the treating physician's expectation and possible confounders are well distributed among the groups. Randomisation will be done using a CDMS (SecuTrial®) by a trained member of the study personnel. All study personnel will be trained and instructed for the study procedures. The primary outcome evaluation is performed by blinded study personnel via telephone interviews, the primary outcome analysis is performed by our blinded trial statistician not involved the treatment plan of the patients. Other forms of reducing bias will be the use of prospective CRF Forms, the use of validated and commonly applied scores (mRS/NIHSS/GCS/PROMIS®/MOCA) for the outcome assessments and blinded laboratory personnel assessing the biomarker results, as the individuals analysing the biomarkers will have no information regarding the treatment plan of the patient. Lastly, regular quality control will take place to ensure that all procedure standards are met. Explorative stratified sub-group analysis accounting for possible confounders mentioned in 3.2 will be conducted.

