3.3.4 Blinding and Unblinding procedures (Code Break)

Since this is a surgical trial, blinding is not possible for primary care providers. However, the laboratory personnel analyzing the biomarkers as well as the statistician will be blinded as these are not directly involved in the patient care or outcome assessment. Laboratory personnel will be blinded to the allocation as only encoded material will be processed where patients are identified by their patient ID, which gives no hint to the allocation. Likewise, the study statistician responsible for the primary analysis will receive a blinded copy of the data sets. Furthermore, we will conduct blinded outcome assessment at 3 and 6-month follow-up through study personnel blinded to the allocation of the patient in form of a standardized telephone assessment (Appendix 4)[35]. This form of assessment is highly comparable with face-to-face evaluation, is short and easy to implement[36].

Since no patient or care provider blinding is possible (due to the study design including a surgical treatment arm), no emergency unblinding is necessary.

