4.3.6 V6: Month 6 assessment: 6 months ± 7 weeks after treatment

Clinical examination is performed as detailed for V1 except for body weight and height and mRS. Blood sampling for biomarkers will be obtained. A cCT will be performed for all patients (control and intervention group) to evaluate possible rebleeding, hematoma resorption and the shape of the hematoma cavity. A MOCA Test is performed. Additionally, a questionnaire regarding patient satisfaction will be filled-out whenever possible through a relative or otherwise together with a member of the study team and patients and their relatives will be asked to fill out a questionnaire together with a member of the study team regarding the quality of life. Additionally, patients are telephonically contacted by a study-team member (blinded to the allocation) to assess the mRS according to the form in Appendix 4.

Study period	Treatment Period				Follow-Up	
Visit	1	2	3	4	5	6

Time (hour, day, week)	<24 hours of symptom onset	24 hours after treatment onset	72 hours after treatment onset	7 days after treatment onset	3 months after treatment onset	6 months after treatment onset
Eligibility	X					
Study consent	X					
Asses vital signs (BP,HR,height)	X	X	X	X	X	X
Acquire NIHSS score	X	X	X	X	X	X
Acquire GCS score	X	X	X	X	X	X
Acquire mRS score	X	X	X	X	X**	X**
Acquire blood samples (NfL, GFAP, S100B, IL)	X		X			X
Conduct Stability CT scan*	X					
Conduct directly postoperative CT scan†		X				
Conduct postinterventional CT scan‡		X				X
Quality of Life					X	X
Patient Satisfaction					X	X
Cognition					X	X

*intervention group only; only required if surgery cannot be initiated within 6 hours after the first cCT scan

†intervention group only; the directly postoperative cCT is conducted directly after surgery to assess hematoma evacuation and differentiate potential recurrent hemorrhage

‡all patients; the postinterventional cCT scan is conducted 24 hours and 6 months after the treatment start to assess potential recurrent/enlarged hematoma and defect size

**blinded telephone assessment

4.3.7 Additional material, storage, concomitant care as well as methods and tests used for sample collection and analysis

The imaging analysis, the additional materials and biomarkers used for this study and the procedure to reverse oral anticoagulation are explained in the following section.

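### Section 5.2 lets a missing 6-month mRS be sought from the treating physician, who knows the allocation, without requiring blinded rating.

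*Protocol*

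**What the plan says.** Section 3.3.2 sets the safeguard: "The primary outcome evaluation is performed by blinded study personnel via telephone interviews". Section 3.3.4 repeats it for months 3 and 6. Section 4.3.6 gives the procedure at the final visit: "patients are telephonically contacted by a study-team member (blinded to the allocation) to assess the mRS according to the form in Appendix 4". The clinic examination at that visit leaves the scale out: "Clinical examination is performed as detailed for V1 except for body weight and height and mRS".

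The clinical side knows the arm. Section 3.3.4 states "Since no patient or care provider blinding is possible", and section 3.3.3 has the allocation sent electronically to the treating team.

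Section 5.2 gives the rule for missing data. First comes recovery: "we will try to obtain the respective data needed from either the participant, their next of kin or their treating physician". Then: "If acquiring the respective missing data is not possible, we will mark the data as missing". The paragraph closes with the primary outcome: "In case more than 5% of patients show missing data for the primary outcome across arms, multiple imputation is performed".

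For patients who leave, section 4.3 analyses data up to the last visit attended, and section 4.4 records withdrawals as lost to follow-up.

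**The concern.** With patients and clinicians unblinded, the main guard against detection bias in the primary outcome is the blinded, standardised rater. Section 5.2 names an informant who knows the allocation as a source for any missing item. It does not exempt the mRS, does not say who rates what is recovered, and does not ask for the source to be recorded. A site that took a missed mRS from the treating physician would comply with 5.2 while departing from 3.3.2, 3.3.4 and 4.3.6.

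The endpoint is one cut, between mRS 3 and 4, and that judgement turns on walking and self-care. A rater who knows the arm could place borderline patients differently by arm. Once entered, the value is an observed outcome. It is not counted as missing for the imputation rule, and it cannot later be told apart from a blinded rating unless the source was recorded.

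**Working it through.** **1. The sections side by side.**

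| Question | 3.3.2, 3.3.4, 4.3.6 | 5.2 |
|---|---|---|
| Who rates the 6-month mRS? | Blinded study personnel | Not stated |
| With what instrument? | Appendix 4 telephone form | Not stated |
| Who may supply the information? | The patient, by telephone | Participant, next of kin or treating physician |
| Is the primary outcome covered? | Yes | Yes, it is not excepted and the same paragraph sets its imputation rule |

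The two columns can both be met if the blinded assessor questions the informant. They conflict if a clinician's own rating is entered. Section 5.2 does not rule out the second.

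**2. The 5% trigger.** At the maximum of 200 patients (section 5.1.2.4), 5% is 0.05 × 200 = 10, so imputation needs at least 11 missing outcomes. Suppose 12 calls are missed and 2 values come from physicians. The count falls to 12 − 2 = 10, which is 5.0%, and the rule is not triggered.

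**3. The plan's own figure, to check the model used in steps 4 and 5.** Section 5.1.2.5 says about 90% of trials reach a Bayes factor (BF) of 10 by 70 per arm, with 50% good outcome under BMT and RR 1.6 (0.5 × 1.6 = 80% under ES). Section 5.1.2.3 uses package default priors without giving values. I assumed standard normal priors on the mean logit β and the log odds ratio ψ:

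- H1: logit p(BMT) = β − ψ/2, logit p(ES) = β + ψ/2
- H0: ψ = 0
- BF = marginal likelihood under H1 ÷ marginal likelihood under H0

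In 20,000 simulated trials tested after every pair of patients, 90.4% reach BF 10 by 70 per arm. The stated figure reproduces and is not affected by this point.

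**4. How close to the threshold one rating can matter.** BMT is fixed at 50%. The ES count is the smallest that gives BF ≥ 10, and is then reduced by one.

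| Per arm | BMT good | ES good | BF | BF with one fewer ES good |
|---|---|---|---|---|
| 40 | 20 | 32 | 11.88 | 6.67 |
| 60 | 30 | 45 | 12.65 | 7.74 |
| 80 | 40 | 57 | 10.04 | 6.62 |
| 100 | 50 | 70 | 13.77 | 9.25 |

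This shows only that a trial at the boundary can turn on one patient. It does not measure bias.

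**5. Illustration of bias, all rates assumed.** There is no true effect (50% in both arms). A share m of outcomes comes from unblinded ratings. Within that share, a proportion b of poor ES outcomes is rated good and a proportion b of good BMT outcomes is rated poor.

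- ES rate = 0.5 + 0.5mb, BMT rate = 0.5 − 0.5mb, false difference = mb
- Looks at 40, 60, 80 and 100 per arm (section 5.1.2.6), 20,000 simulated trials. Exact enumeration agrees to within 0.1 percentage point.
- The last column is the two-sided 5% test of proportions at 100 per arm, counting rejections in favour of ES.

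| m | b | False difference | BF ≥ 10 for ES | Frequentist test favours ES |
|---|---|---|---|---|
| none | none | 0 | 0.8% | 2.8% |
| 5% | 10% | 0.5 points | 0.9% | 3.3% |
| 5% | 25% | 1.25 points | 1.2% | 4.1% |
| 10% | 25% | 2.5 points | 1.7% | 6.0% |
| 10% | 50% | 5 points | 3.6% | 11.4% |
| 20% | 50% | 10 points | 12.7% | 31.0% |

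Neither m nor b can be read from the protocol.

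**The case against.** The strongest reply is that 5.2 is a general clause for every kind of missing item. It says only that the team will try, it lists the physician last of three informants, and it does not say who rates the mRS. The rater is fixed in 3.3.2, 3.3.4 and 4.3.6, and a blinded assessor who telephones a relative or physician would satisfy every section. This stands. A reader might infer that 5.2 fills a missing mRS from the physician; the text allows that but does not direct it.

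Three further inferences are not supported:

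- **Patients who leave the trial.** Sections 4.3 and 4.4 stop their data at the last visit and mark withdrawals as lost to follow-up. The firm case is the patient still in follow-up who misses the call. Section 5.2 also has drop-outs in its heading, so the three sections should be reconciled.
- **The treating physician as the surgical or stroke team.** Section 5.2 does not define the term, and section 4.2 mentions referring family physicians and peripheral hospitals. The trial's own clinicians are not excluded, but that is all the text shows.
- **One or two ratings triggering a stop, read as a measure of bias.** Any threshold rule flips when a patient is removed at its edge, and a random scoring error would do the same.

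It is also fair to say that patients, and perhaps relatives, know the arm, so what is at risk is the blinded rating rather than an uninformed source. The clinic visit generates no 6-month mRS to hand over, and the window of ±7 weeks leaves room for repeat calls. The eCRF audit trail records who authorised an entry, though not who supplied the information. The detail of a sensitivity analysis may properly sit in a statistical analysis plan. The recovery rule, however, is stated in the protocol itself.

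**Conclusion.** The point holds as a gap in a stated rule. Section 5.2 permits an unblinded 6-month mRS to enter as an observed primary outcome and to stay outside the 5% imputation trigger, which does not fit the blinded assessment promised elsewhere. Its size cannot be given, because the protocol states neither a missing rate nor how recovered values would be rated. Over the assumed ranges (m from 5% to 20%, b from 10% to 50%, assumed standard normal priors) the effect runs from negligible to material, and the upper end needs a fifth of outcomes to be unblinded with half of those tilted. The sample size and the stated 90% are unaffected. The change is worth making because it costs almost nothing and cannot be made good after unmarked values have been entered.

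**What to change.** In section 5.2, state that any recovered 3- or 6-month mRS is collected and rated only by the blinded telephone assessor using the Appendix 4 form, with the participant, next of kin or another informant. State that no mRS rating is taken from the treating stroke or neurosurgical team, apart from the fact and date of death. Add an eCRF field for the informant, and repeat the primary analysis without proxy-derived values as a sensitivity analysis. Reconcile 5.2 with 4.3 and 4.4, so that it is clear whether recovery applies to patients who drop out or withdraw.

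The cost is a few sentences, one eCRF field and one extra analysis; the blinded assessor and the form already exist. The downside is that a few values the clinic could have supplied may stay missing. These would then count towards the 5% trigger.
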